**MRI and MRS scanning:**

Subjects will undergo MRS scanning at 4T at 0, and 12 weeks of the study. Scan time is ~45 minutes. After a T1 weighted MRI for anatomy (gray/white/CSF segmentation), glucose and fructose concentrations will be obtained from ~3X3X3 cc voxels. Signals from respective voxels are isolated using a MEGA PRESS-based sequence. Metabolite levels are measured by spectral fitting using a simulated basis set and referenced to total voxel water signal and creatinine to determine concentration.

[figure not shown]
During each of these two scans, plasma glucose, fructose, insulin, HbA1c, and fructosamine levels will be measured concurrently.

A nurse experienced with working in a MRS environment will be with subjects at all times. Vital signs including heart rate and blood pressure will be monitored prior to scanning. If patients express discomfort or anxiety and ask to be removed from the scanner, the session will be immediately terminated.

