**Optional Hyperglycemic clamp:**

Prior to MRS scanning at weeks 0 and 12 Subjects may also be invited to participate in an optional overnight admission to normalize blood glucose levels the night before scanning and then a hyperglycemic clamp the following morning.

Subjects will be admitted in the evening prior to MRS scan day (~ 6 PM) to the YNHH research unit, all of their diabetic medications will be held and they will be placed on an insulin drip beginning at 8PM to maintain blood sugar levels at ~90-100 mg/dl until 7AM the next morning. The next morning, participants will be taken to the MRRC for MRS scanning. Following the 45 minute

baseline scan, subjects will remain in the scanner for continuous scanning during the hyperglycemic clamp (see figure). An infusion of 20% dextrose at a variable rate to maintain plasma glucose levels at 220 mg/dL for 4 hours. Glucose infusion rates will be adjusted in response to plasma glucose levels measured every 5-10 minutes. Subjects will be able to take breaks as needed during the 3 hours hyperglycemic clamp and MRS scan. At baseline, 2 and 4 hours, plasma samples will also be obtained for fructose, sorbitol, insulin levels and other hormonal markers.

**Continuous glucose monitoring system (CGMS) and Food logs (at -1, and 11 weeks):** One week prior to the MRS scans at 0 and 12 weeks, subjects will be asked to wear a CGMS (Free style libre) to continuously monitor their interstitial blood glucose levels and record their food intake

**Blood collection for platelet and inflammation analysis:** Participants will also have blood collected (~80 cc) for analysis of polyol pathway activity in platelets as well as for changes in inflammatory markers such as cytokines IL-6, TNF-alpha at weeks 0, and 12 weeks.

**Optional Specimens for Future Storage:** Subjects will be asked to give permission for the storage of any blood obtained during the study that will not be used for the above noted analysis

**4. Genetic Testing** N/A

**5. Subject Population:** Provide a detailed description of the types of human subjects who will be recruited into this study.

15 T2DM subjects with HbA1C > 7.5%

15 T1DM subjects with HbA1C > 7.5%

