**Plan for reporting adverse events to co-investigators on the study, as appropriate the protocol's research monitor(s)**

For the current study, the following individuals, funding, and/or regulatory agencies will be notified (choose those that apply):

All Co-Investigators listed on the protocol.

National Institutes of Health

The principal investigator ([name]) will conduct a review of all adverse events upon completion of every study subject. The principal investigator will evaluate the frequency and severity of the adverse events and determine if modifications to the protocol or consent form are required.

**12. Statistical Considerations:** Describe the statistical analyses that support the study design.

**Primary endpoints:** Primary endpoints include (a) HbA1C levels and CGM measures of glycemia; (b) baseline intracellular fructose and glutathione levels at 0, and 12 weeks; (c) intracellular fructose and glutathione levels following hyperglycemic clamp at 0 and 12 weeks.

**Secondary endpoints:** Concentrations of hormones and polyol metabolites will be correlated with structural changes/inflammatory changes on MRI.

**Sample size:** Because endogenous intracellular fructose production in the brain has never been shown in humans, the studies described in this proposal are exploratory studies. As such, sample sizes and statistical comparisons may not provide adequate power for definitive hypothesis testing. Because intracellular polyol levels will likely be equal to or higher than CSF levels, we expect that the percentage changes as measured by MRS will match those (or be even larger) than observed in CSF.

**Statistical analysis:** Before statistical testing, all variables will be tested for normality of distribution. For between-group comparison, ANOVA and t-tests will be used for continuous variables. Within subject comparisons at baseline and following hyperglycemia will be made with paired t-tests (parametric) and Mann-Whitney U (non-parametric) as well as repeated measures ANOVA as appropriate.

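### The rank test named for within-subject comparisons, Mann-Whitney U, is for independent samples and discards the pairing

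*Combined protocol and SAP*

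**What the plan says.** The statistical analysis paragraph of Section V, item 12 begins with a screening step: "Before statistical testing, all variables will be tested for normality of distribution". It gives no test, cutoff or rule for what follows from a failure.

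For comparisons between groups it says: "For between-group comparison, ANOVA and t-tests will be used for continuous variables". No rank test is named there.

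For comparisons within a subject it says: "Within subject comparisons at baseline and following hyperglycemia will be made with paired t-tests (parametric) and Mann-Whitney U (non-parametric"), followed by "as well as repeated measures ANOVA as appropriate".

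The design produces paired data in two ways. In Section V, item 3, the MRI and MRS paragraph says: "Subjects will undergo MRS scanning at 4T at 0, and 12 weeks of the study". The clamp paragraph says that after the "baseline scan, subjects will remain in the scanner for continuous scanning during the hyperglycemic clamp", so the values before and during the clamp come from one person in one session. The clamp is voluntary: "Subjects may also be invited to participate in an optional overnight admission to normalize blood glucose levels".

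The primary endpoints in item 12 include "baseline intracellular fructose and glutathione levels at 0, and 12 weeks", and the same two metabolites after the clamp at both visits.

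**The concern.** The sentence calls the comparison within-subject and then offers two tests as parametric and non-parametric counterparts. The first uses the pairing; the second does not. Mann-Whitney U judges the shift against the spread between people. A paired test judges it against the spread of each person's change, which is smaller when the two measurements are positively correlated.

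The loss would fall on a small study. Enrolment is 15 subjects per diabetes type, and because the clamp is optional there may be fewer clamp pairs than that. Brain fructose and glutathione after the clamp are a primary endpoint, and part of the hypothesis in Section V, item 1 concerns the fructose response to the clamp. The plan already warns that power may be inadequate, so it has little sensitivity to give away.

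**Working it through.** **Inputs from the document.** The tests are those quoted above. There are 15 subjects with type 1 and 15 with type 2 diabetes. There is no power statement to reproduce: alpha, effect size, SD, within-subject correlation, normality test and clamp uptake are not given.

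**Assumptions.** Two-sided alpha is 0.05. The within-subject correlation ρ is 0.3, 0.5, 0.7 or 0.8. There are 15 pairs (one diabetes type, full uptake) or 10 pairs (partial clamp uptake).

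**Step 1: direction of the error.** Under no change, positive correlation shrinks the true variance of the Mann-Whitney statistic by a factor of roughly 1 − ρ, while the test uses the independent-samples variance. In large samples the actual size is therefore about 2[1 − Φ(1.96/√(1 − ρ))]:

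- ρ = 0.3: 1.96/√0.7 = 2.34, size about 1.9%
- ρ = 0.5: 1.96/√0.5 = 2.77, size about 0.6%
- ρ = 0.7: 1.96/√0.3 = 3.58, size about 0.03%
- ρ = 0.8: 1.96/√0.2 = 4.38, size about 0.001%

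Simulation at 15 pairs (20,000 bivariate-normal trials per cell) gives 1.9, 0.8, 0.1 and 0.02%. The nominal 5% test is conservative throughout.

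**Step 2: power when the rank branch is used.** The shift is set so that the paired t-test has 80% power: a standardised mean difference dz of 0.778 at 15 pairs and 0.996 at 10 pairs. (Check at 15 pairs: noncentrality 0.778 × √15 = 3.01 against a critical t of 2.14 on 14 df gives 80%.) In units of the SD between people, the shift is dz × √(2(1 − ρ)). At 15 pairs this is 0.92, 0.78, 0.60 and 0.49 for the four values of ρ. The paired power stays fixed while the shift that Mann-Whitney can see shrinks.

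| ρ | Mann-Whitney, 15 pairs | Mann-Whitney, 10 pairs | Signed-rank, either n |
|---|---|---|---|
| 0.3 | 67% | 68% | 78% |
| 0.5 | 51% | 52% | 78% |
| 0.7 | 25% | 28% | 78% |
| 0.8 | 11% | 14% | 78% |

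At ρ = 0 nothing is lost (15 pairs: 79% against 77%).

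**Step 3: power of the whole procedure.** Only variables that fail the normality screen reach the rank test. Because the plan gives no rule, assume Shapiro-Wilk at p < 0.05. The table gives the percentage points of power lost by having Mann-Whitney rather than signed-rank as the fallback, for ρ = 0.3/0.5/0.7/0.8 (6,000 trials per cell; lognormal data have log-SD 0.5 and the same standardised shift on the log scale).

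| Screen applied to | Pairs | Normal data | Lognormal data |
|---|---|---|---|
| Either time point | 15 | 1/2/4/5 | 4/14/29/36 |
| Either time point | 10 | 1/2/4/5 | 2/10/17/22 |
| Paired differences | 15 | 1/1/3/4 | 2/6/14/18 |

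With 15 pairs and the screen on either time point, the rank branch is taken in 9 to 10% of trials with normal data and 56 to 63% with lognormal data. At ρ = 0 the version with Mann-Whitney is 0 to 4 points ahead, so the loss requires positive correlation.

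**Step 4: a different effect size.** With a fixed shift of 0.5 SD on the log scale (log-SD 1), 15 pairs, ρ = 0.7 and the rank test always used, power is 0.14 for Mann-Whitney and 0.55 for signed-rank. With 8 pairs it is 0.05 against 0.27. Across the correlations tried (0 to 0.9), signed-rank size at 15 pairs stayed between 0.045 and 0.051.

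**The case against.** The strongest reply is that this is a slip of the pen. The authors may have meant signed-rank, or Mann-Whitney may belong in the between-group sentence, which has no rank option. The document does not settle which. Either reading explains the error, but the text still prescribes the wrong test and needs correcting.

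The second reply concerns reach. The sentence most naturally describes the contrast before and during the clamp, which is optional. The study's stated aim is week 0 versus week 12, and item 12 gives that contrast no explicit test. This stands: the fault reaches the main aim only if the same sentence is meant to cover it.

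The third concerns size. The powers in step 2 assume that the rank test is always used on normal data, where the assumed screen would choose it in about one trial in ten. The large losses in step 3 need skewed data, at least moderate correlation and a particular screening rule, none of them in the document. This also stands, so step 3 is the better guide to the expected effect. Pooling both types (30 pairs) does not remove the problem: losses under the two-stage rule are about 1 to 6 points for normal data and 7 to 59 for lognormal data.

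Finally, the study calls itself exploratory, and the error is conservative under positive correlation. That lowers the stakes. Repeated measures ANOVA keeps the pairing but is parametric, so it does not repair the rank branch.

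**Conclusion.** The concern holds. The plan assigns an independent-samples test to paired comparisons and names no paired rank test elsewhere. The fault is confined to the rank branch of the within-subject analysis; the paired t-test and repeated measures ANOVA are unaffected.

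The consequence is lost sensitivity. With positive correlation the type I error falls below its nominal level; inflation would need negative within-subject correlation. The likely loss ranges from negligible (correlation near zero) through a few points (near-normal data) to 36 points (lognormal data, 15 pairs, ρ = 0.8, screen on either time point). These figures illustrate an assumed range and do not predict this trial's power. The correction should be made before analysis.

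**What to change.** In the within-subject sentence of Section V, item 12, replace Mann-Whitney U with the Wilcoxon signed-rank test. Add one sentence stating that the same paired tests apply to week 0 versus week 12 and that normality is checked on the paired differences. If a rank comparison of type 1 with type 2 diabetes is wanted, Mann-Whitney U can be named in the between-group sentence, where it fits.

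The cost is one phrase and one sentence, with no new data and no change to visits or measurements. One caution: as a test of location, signed-rank assumes roughly symmetric differences, so a skewed variable may need a log transform first.

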#### Study design:

**Subjects:** 15 T2DM subjects and 15 T1DM subjects with HbA1C > 7.5% will be recruited from Yale New Haven Hospital and the greater New Haven area.

**Inclusion criteria:** Age 18- 65 yrs, BMI  $\geq 18$  kg/m^2, and weight less than 285 pounds (upper limit of scanner),

**Exclusion criteria:** Creatinine > 1.5 mg/dL, Hgb < 10 mg/dL, hematocrit of 37 % for males participants and 33 % for female participants, ALT > 3 x ULN, , untreated thyroid disease, uncontrolled hypertension, known neurological disorders, untreated psychiatric disorders, malignancy, bleeding disorders, current or recent steroid use in last 3 months, illicit drug use; for women: pregnancy, actively seeking pregnancy, or breastfeeding; inability to enter MRI/MRS (per standard MRI safety guidelines).

**Screening visit:** Volunteers will be screened at the YNHH Research Unit (HRU) with a medical history and exam including detailed neurologic exam. Blood tests will be collected for A1C, ALT, TSH, Hematocrit. Less than 35 mL of blood will be drawn for blood work. Women will undergo urine pregnancy testing. Subjects will be required to give us information about their substance use/HIV status because this can affect brain glucose metabolism.

**Intensification of Insulin regimens:** The intensification of the diabetes regimens will be managed by [name], a fully trained attending endocrinologist, and will follow the general strategies outlined in the Position Statement of the American Diabetes Association and the European Association for the Study of Diabetes. All participants will receive exercise and dietary counseling from [name], a nutritionist and registered dietician with extensive

experience with working with individuals with diabetes and obesity. Participants will communicate with a nutritionist regularly over the course of the 12-week study.

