**Targeted Enrollment: Give the number of subjects:**

- a. targeted for enrollment at Yale for this protocol: 30 subjects total
- b. If this is a multi-site study, give the total subjects targeted across all sites: N/A

2. **Indicate recruitment methods below.** Attach copies of any recruitment materials that will be used.

- |   |  |                                     |
|---|--|-------------------------------------|
|  Flyers                                     |  Internet/Web Postings                                      |  Radio      |
|  Posters                                    |  Mass E-mail Solicitation                                   |  |
| Telephone  Letter                           |  Departmental/Center Website                                |             |
| Television  |  |                                     |
|  Medical Record Review           |  Departmental/Center Research Boards                        |  Newspaper  |
|  Departmental/Center Newsletters |  Web-Based Clinical Trial Registries                                   |                                     |
|  YCCI Recruitment database       |  Clinicaltrials.gov Registry (do not send materials to HIC) |                                     |
|  Other (describe): Mychart, JDAT            |  |                                     |

3.

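### Classical repeated measures ANOVA on the optional clamp series would drop every partly observed subject; the plan should name a model that uses all observed time points, though the size of the loss is unknown.

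*Combined protocol and SAP*

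**What the plan says.** All references are to the Combined protocol and SAP.

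- **Tests.** Section V, item 12 (Statistical analysis) lists "paired t-tests (parametric) and Mann-Whitney U (non-parametric) as well as repeated measures ANOVA as appropriate". The sentence ties these tests to baseline versus after hyperglycemia. It names no test for week 0 against week 12, no analysis population, no missing-data method and no rule for a partial session.
- **Endpoint.** The third group of primary endpoints in the same item is "c) intracellular fructose and glutathione levels following hyperglycemic clamp at 0 and 12 weeks".
- **Series.** Section V, item 3 (Optional Hyperglycemic clamp) describes continuous scanning through the clamp and plasma at baseline, 2 and 4 hours, at weeks 0 and 12. It does not say how many MRS time points will be analysed.
- **Interruptions.** The same section says "Subjects will be able to take breaks as needed during the 3 hours hyperglycemic clamp and MRS scan". MRI and MRS scanning adds: "If patients express discomfort or anxiety and ask to be removed from the scanner, the session will be immediately terminated".
- **Sample.** Section VII gives "targeted for enrollment at Yale for this protocol: 30 subjects total", 15 per diabetes type. The clamp is by invitation: "Subjects may also be invited to participate in an optional overnight admission to normalize blood glucose levels". No expected uptake is stated.

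**The concern.** The clamp data are repeated times within visit within subject. Classical repeated measures ANOVA needs every cell of that grid, so a subject who stops early at one visit loses all the other values too. None of the named methods uses a partial series.

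Two things are at stake. One is precision, in a subsample that may be far smaller than 30. The other is selection: those removed are the people who tolerate the scanner least, so the complete cases need not represent the clamp group. Complete-case analysis is safe only if loss is unrelated to anything that affects the outcome.

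**Working it through.** **The plan's own figure.** Only 15 + 15 = 30 can be reproduced. No alpha, power, effect size, SD, dropout rate or clamp uptake is stated, so every rate below is an assumption.

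**1. Complete clamp subjects.** Assume 50% uptake, giving 15 subjects, and let m be the share of sessions cut short at each visit. Complete subjects = 15 × (1 − m)²:
- m = 10%: 15 × 0.81 = 12.2
- m = 20%: 15 × 0.64 = 9.6
- m = 30%: 15 × 0.49 = 7.4

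Under the 50% assumption optional participation removes 15 of 30. Deletion at m = 10% removes 15 − 12.2 = 2.8 more.

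**2. Precision of the change in clamp rise (week 12 minus week 0).** With complete cases the standard error (SE) grows by about √(15 / complete subjects) = 1 / (1 − m), which is 1.11, 1.25 and 1.43. Simulation gives slightly more, because the number complete varies from trial to trial. Its assumptions are 5 bins per visit, subject SD 1, visit SD 0.5, residual SD 0.6, and at least one bin observed in a cut session. SE ratios to full data:

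| Sessions cut short | Complete cases | All available data, known covariance |
|---|---|---|
| 10% | 1.12 to 1.16 | 1.02 to 1.04 |
| 20% | 1.28 to 1.29 | 1.04 to 1.09 |
| 30% | 1.49 to 1.50 | 1.05 to 1.15 |

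Ranges cover separate runs. In the last column they also cover the definition of the rise: the lower end is for the clamp mean minus baseline, the upper end for the final bin minus baseline.

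**3. Three-point series (2 visits × 3 times, as for plasma).** With early termination, the complete-case variance of the 4-hour rise is about 1.14, 1.32 and 1.56 times the all-data variance at m = 10, 20 and 30%. Taking square roots, the SE ratios are 1.07, 1.15 and 1.25.

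**4. Scattered gaps, the worst pattern for deletion.** If each of 10 cells is missing independently, complete subjects number 15 × 0.95¹⁰ = 9.0 at 5% and 15 × 0.90¹⁰ = 5.2 at 10%. The SE ratios are then about 1.34 and 1.8 with complete cases, against about 1.04 and 1.08 with all data.

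**5. One scan per visit, week 0 against week 12.** If scans are lost at random at either visit, pairs = 30(1 − m)² and single scans = 30m(1 − m) at each visit. With between-visit correlation ρ, the variance ratio (complete pairs to all data) is 1 + m(1 − ρ)/(1 − m):
- ρ = 0.7: 1.03, 1.08, 1.13 at m = 10, 20, 30%
- ρ = 0.3: 1.08, 1.18, 1.30

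The largest of these is an SE ratio of √1.30 = 1.14. Here the loss comes mainly from the absent scan, not from the test.

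**The case against.** A reader might infer that the named tests will discard much of the sample of 30. The documents do not support that. They give no rate of breaks, terminations, withdrawal or uptake. With 5% of sessions lost per visit, 30 × 0.95² = 27.1 pairs remain; with 10%, 24.3. A break is not in itself a missing value: the subject can return, bins can be averaged around the gap, and nothing says that plasma sampling stops. Early termination, which does lose data, does not produce the scattered pattern of step 4.

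A reader might also carry the point over to the week 0 versus week 12 comparison. The plan's sentence does not name that comparison, and step 5 shows that little would be recovered.

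The wording of item 12 leaves the choice of test open and does not prescribe deletion. A paired t-test on each subject's available clamp mean minus baseline uses a method already named and has SE ratios of about 1.04 to 1.17. The study also calls itself exploratory and concedes limited power.

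All of this stands, and it limits the claim. It does not remove the gap. The plan never says that the series will be reduced to an available-data mean, and if fructose keeps rising, the mean of a session cut short describes only the early clamp. Limited power is a reason to keep collected data.

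**Conclusion.** The point holds for the clamp MRS and plasma series. If repeated measures ANOVA is applied to them in its classical form, partly observed subjects are lost, and the plan offers no alternative and no rule for them. The size is unknown. Under the assumptions of step 2, complete-case SEs are roughly 1.1 to 1.5 times the full-data value, and most of that excess is recoverable. The recoverable share is somewhat optimistic, because the covariance was treated as known and loss as completely at random.

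The point is minor for single-scan comparisons between visits. Optional uptake may cost the clamp endpoint more subjects than the choice of test. This is a change worth making to the analysis text, not a flaw that invalidates the design.

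**What to change.** In Section V, item 12, for the clamp MRS and plasma series:

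- Replace repeated measures ANOVA with a linear mixed model per outcome, fitted by REML with Kenward-Roger degrees of freedom to all observed time points. Fixed effects: visit, time, visit × time and diabetes type.
- Let the clamp rise vary between subjects and visits, through a random rise as well as a random intercept, or an unstructured covariance over a few pre-set bins. Intercepts alone are not enough: in simulation the type I error for the visit-by-rise contrast was about 6% at a between-subject rise SD of 0.3 and 9% at 0.5, against about 5% for the paired t-test. An unstructured matrix needs few bins: 2 visits × 3 bins has 6 × 7 / 2 = 21 parameters, and 2 × 5 has 10 × 11 / 2 = 55, too many for a sample of this order.
- Name the fallback if the model does not converge: a paired t-test on each subject's available clamp mean minus baseline.
- For baseline-only scans use a random subject effect alone. With one scan per visit, a visit-within-subject term cannot be separated from residual error.
- Define a usable session and the time bins in advance. Report the number contributing to each endpoint and the reasons for missing data. The clamp is given as both 4 and 3 hours long; these statements must be reconciled before a complete series can be defined.

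The cost is SAP wording and standard software, with no added visits or subjects. The downside is that a covariance structure must be assumed and the analysis relies on missing at random. Termination for discomfort may violate that, so the mixed model reduces the selection problem without curing it.
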